heart disease in HIV is greater compared to the general population. We have demonstrated significant RAAS activation in HIV patients with metabolic abnormalities, including increased visceral adiposity and insulin resistance, and suggest that this unique physiology may contribute to a metabolic phenotype that is pro-inflammatory, pro-fibrotic, and pro-atherogenic. It is plausible that a cascade of excess MR activation in HIV potentiates cardiac injury and dysfunction. Moreover, there is relevant data to support testing the efficacy of MR blockade in managing impaired myocardial perfusion, myocardial fibrosis, diastolic dysfunction, and plaque. The grant will provide new mechanistic insight and enhance our understanding of CVD in HIV. We will take advantage of advanced imaging methods to permit a non-invasive longitudinal assessment of structural and functional CV defects in HIV to add new information to the field. This is an ideal proposal aiming to integrate several manifestations of CVD in HIV through a novel hormone pathway. The clinical utility of MR blockade could have far reaching effects towards overall CV risk reduction in HIV, and such studies could serve as a model for other at-risk metabolic groups.

II. Specific Aims

We will perform a randomized double-blind study among HIV subjects with increased visceral adiposity and subclinical atherosclerosis, administering eplerenone vs. placebo for 12 months. We will provide all subjects with lifestyle modification throughout the study. We hypothesize that adding eplerenone to lifestyle modification will significantly improve key indices of cardiac structure and function.

Among the large population of HIV patients in whom we have shown renin-angiotensin-aldosterone activation and subclinical atherosclerosis, we will determine:

❖ **Specific Aim I: The effect of MR blockade on myocardial perfusion.**

We hypothesize:

- a) MR blockade will improve coronary flow reserve (CFR) on cardiac positron emission tomography (PET) or stress myocardial blood flow (sMBF) on cardiac magnetic resonance imaging (MRI).
- b) MR blockade will reduce markers of vascular dysfunction.

❖ **Specific Aim II: The effect of MR blockade on myocardial inflammation and fibrosis.** We hypothesize:

- a) MR blockade will reduce myocardial extracellular volume fraction, a measure of myocardial fibrosis and inflammation, assessed by serial myocardial T1 mapping cardiac magnetic resonance imaging (MRI).

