Statistical Consideration: Aim I: The primary endpoint is change in CFR assessed by cardiac PET or change in sMBF by cardiac MRI. Secondary endpoints will include the following: change in sICAM and sVCAM. Shapiro-Wilk test will be used to assess for normality of distribution, and variables that are not normally distributed will be appropriately transformed prior to inclusion in multivariable models. We will compare the change in CFR from months 0 to 12 between treatment groups (eplerenone vs. placebo) using student's t-test for variables that are normally distributed or Wilcoxon rank sum test for variables that are not normally distributed. We will also compare changes in sICAM and sVCAM over 12 months between treatment groups using similar statistical methods. In all Aims, for subjects who withdraw after 6 months, but before the final 12 month visit, we will obtain biomarkers and imaging similar to that scheduled for the final 12 month visit if the subject agrees to have end of study testing. The analysis will be intention to treat (ITT). In order to properly handle subjects with missing outcomes (those who withdrew before 12 months), we will apply longitudinal linear mixed effects model analysis with random subject level intercepts and time slopes by which the longitudinal treatment effect can be examined by testing the significance of

Mineralocorticoid Receptor Antagonism for Cardiovascular Health in HIV The MIRACLE HIV Study

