time x treatment interaction, which will provide unbiased effect estimate under missing at random condition, which will be carried out by using augmented data sets created by multiple imputation. A sensitivity analysis will be performed to include only those subjects who completed the study. Baseline variables will be compared between treatment groups, and any variable that is statistically different between groups will be controlled for using multivariable modeling. It may be that subjects with more significant RAAS activation and dysregulation in aldosterone at baseline) are more responsive to eplerenone. We will phenotype the RAAS in subjects at the low sodium visit and, guided by this data, may use aldosterone levels prior to intervention as an index of RAAS activation and a covariate in assessing treatment response, to determine if eplerenone is more effective in the subpopulation with greater baseline aldosterone dysregulation and RAAS activation. Covariates that will be considered for inclusion in modeling, include variables that differ at baseline and those variables that may affect vascular dysfunction, inflammation, fibrosis and plaque (age, race, gender, BP, tobacco/illicit drug use, family history of CVD, lipids, and glucose), HIV parameters (viral load, CD4, and duration of HIV and ART use) and compliance. This will permit us to assess relevant factors that may mediate the effect of eplerenone on CFR in HIV and interactions between HIV and traditional risk factors contributing to eplerenone effects. Moreover, we will compare changes in CFR and vascular biomarkers over 12 months using regression analysis. We will perform Pearson's correlation for variables that are normally distributed and Spearman's correlation for variables that are non-normally distributed. If we see significant changes in specific biomarkers that correlate with changes in CFR, then we will run those specific biomarkers from stored serum at earlier time points (e.g. 6 months) to see if early changes in biomarkers can predict changes in CFR, as well as predict response to MR blockade. **Biostatistician Role:** The biostatistician will monitor data collection, quality and completeness of the study throughout all years of the grant. The biostatistician will create the randomization plan, using a permuted block algorithm, stratified for gender, statin use, and presence of plaque and provide the list to the study pharmacist (investigators will remain blinded). Identical placebo will be provided by the pharmacy. **Sample Size Determination:** Preliminary data from HIV subjects presented in this grant demonstrate a CFR 1.74 ± 0.73 (mean \pm SD) using cardiac PET. Supportive data are also derived from a longitudinal study by our team using cardiac PET, showing mean \pm SD change of CFR in diabetics treated with spironolactone 0.33 ± 0.83 vs. placebo: 0.02 ± 1.03 over 6 months (mean SD=0.93).⁴⁰ Given these data, we considered the range 0.73 - 0.93 SD to accurately reflect the potential variability of change in CFR for the proposed study. Based on this data, we now provide a range of detectable differences using 85% power and a revised increased sample size of 80 subjects, with an attrition rate of 15%, leaving 68 evaluable subjects. Thus, even choosing a conservative SD of 0.93, the study will be well powered to detect a difference in mean change of CFR of at least 0.69. As our preliminary data, using PET, show that HIV patients have a mean CFR 1.7, an increase of CFR to 2.4 with eplerenone is a clinically relevant increase associated with decreased morbidity and mortality. For the sMBF and biomarkers, this study has 85% power at a two-sided 0.05 α level to show a change in the variable of at least 0.74 SD after treatment with eplerenone vs. placebo.

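### Aim I joins CFR by PET and sMBF by MRI as its primary endpoint with *or* and no deciding rule; if either may count, the two-sided false-positive rate exceeds 5% and can reach 9.75%

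*Combined protocol and SAP*

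**What the plan says.** Section VI, Aim I, defines the endpoint: "The primary endpoint is change in CFR assessed by cardiac PET or change in sMBF by cardiac MRI". Section II, Specific Aim I, hypothesis a, has the same alternative; it predicts improvement in "coronary flow reserve (CFR) on cardiac positron emission tomography (PET) or stress myocardial blood flow (sMBF) on cardiac magnetic resonance imaging (MRI". The section VI sentence after the definition reads "Secondary endpoints will include the following: change in sICAM and sVCAM", so sMBF is not on the secondary list.

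The between-group test is described for one measure only: "We will compare the change in CFR from months 0 to 12 between treatment groups". The Aim I sample-size paragraph then treats both. For CFR it concludes that "the study will be well powered to detect a difference in mean change of CFR of at least 0.69", using an SD of 0.93 and 68 evaluable subjects. For the other measure it says: "For the sMBF and biomarkers, this study has 85% power at a two-sided 0.05 α level", with a detectable change of 0.74 SD.

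Both measures are to be acquired. Section V schedules cardiac PET for CFR and a cardiac MRI at Baseline Visit 1 and repeats them at 12 months. The Cardiac MRI procedure plans quantified rest and stress perfusion alongside PET, although the Baseline Visit 1 list of MRI outputs does not name sMBF. The COVID-19 contingency plan first allows a delayed visit with extra study drug, and then allows an on-site procedure to be left out. The missing-data text is directed at "subjects with missing outcomes (those who withdrew before 12 months".

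**The concern.** CFR is a ratio of stress to rest flow; sMBF is a stress flow measured on another scanner. A treatment could move one and not the other, so *or* has to be resolved before anyone sees results. It can be read in at least three ways:

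1. CFR decides, and sMBF is supportive.
2. sMBF stands in when PET is unavailable.
3. Significance on either measure is success, or the measure is chosen once results are known.

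A fourth reading, that both must succeed, fits the word *or* least well. The plan writes none of these and excludes none.

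This is the only endpoint in section VI that is called primary. If Aim I is reported as positive on one measure, a reader could not tell whether that measure was prespecified as decisive or picked from two. Under reading 3 the claim does not have the 5% error rate that the power statements imply.

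**Working it through.** **Inputs.** From section VI, Aim I: 80 enrolled, 15% attrition, 85% power, SD of CFR change 0.93, detectable CFR difference 0.69, detectable sMBF change 0.74 SD at two-sided 0.05. Allocation is 1:1 (section IV). The correlation between the two test statistics is not given and is varied below.

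**Reproducing the plan's figures.** 80 × 0.85 = 68, or 34 per arm. Power of a two-sample t-test is P(|T| > t(1 − α/2; 2n − 2)), where T is noncentral t with noncentrality d√(n/2).

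- CFR: d = 0.69/0.93 = 0.742, n = 34, α = 0.05: power 85.4%.
- sMBF: d = 0.74, n = 34, α = 0.05: power 85.2%.
- Smallest difference with 85% power: 0.7375 SD, and 0.7375 × 0.93 = 0.686 for CFR.

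Both stated figures reproduce. The CFR sentence gives no alpha, but 0.69 fits 0.05 (0.686) and not a split alpha of 0.025, where the detectable difference is 0.8105 × 0.93 = 0.754. Each measure is therefore powered at a full, unsplit 0.05.

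**Error rate if either may count.** With two jointly normal statistics of correlation ρ, the rate is 1 − P(|Z₁| < 1.96 and |Z₂| < 1.96). At ρ = 0 this is 1 − 0.95² = 0.0975. The benefit-direction column counts only false claims that eplerenone helps; at ρ = 0 it is 1 − 0.975² = 0.0494, against a nominal 2.5%.

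| Assumed ρ | Two-sided error | Benefit direction only |
|---|---|---|
| 0 | 9.75% | 4.94% |
| 0.5 | 9.07% | 4.54% |
| 0.9 | 7.04% | 3.52% |
| 0.95 | 6.46% | 3.23% |
| 0.99 | 5.66% | 2.83% |

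A null simulation with 34 per arm (200,000 trials) gave 9.7%, 9.0% and 7.1% at ρ = 0, 0.5 and 0.9.

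**Error rate under controlled rules.** In simulation:

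- CFR first, then sMBF only if CFR succeeds: 5.0%.
- Hochberg on both: 5.0%, 4.7% and 4.2% at ρ = 0, 0.5 and 0.9.
- Switching to sMBF blind to outcomes (assumed 30% chance of a switch): 4.9% to 5.0%.

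The inflation thus comes from the lack of a rule, not from measuring both.

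**The case against.** The strongest reply is that the plan already points to CFR. The test sentence names only CFR. The reasoned SD, the detectable difference and the clinical-relevance argument are for CFR. The covariate and biomarker analyses relate to CFR, and Aim III relates plaque to CFR. sMBF has no SD and no clinical threshold, and its power sentence groups it with the biomarkers. No sentence says that success on either measure is enough.

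All of that is correct, and it makes reading 1 plausible. It does not settle the matter, because the sentence that defines the primary endpoint says something else. If CFR was meant, *or* is wrong and should go.

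The size can also be challenged, fairly. 9.75% is a ceiling that requires uncorrelated tests. CFR and sMBF share stress flow, so positive correlation is likely and the figure would be lower. The ceiling also assumes joint normality; with no assumption on dependence the bound is 10%.

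The missing-scan strand is weaker. The contingency plan would lose MRI as well as PET, so it is not evidence that substitution was intended. A generous reader could also apply the mixed model and imputation ("which will provide unbiased effect estimate under missing at random condition") to a subject who stays in the study without a month-12 PET. What stands is that the text limits missing outcomes to withdrawals and does not say whether an MRI value may be used instead.

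**Conclusion.** The concern holds. The Aim I primary endpoint is undefined between two measures, each powered at an unsplit two-sided 0.05. If either may count, the two-sided error rate is above 5% for any correlation strictly between −1 and 1, and at most 9.75% under joint normality. If CFR alone decides, or if sMBF replaces PET under a rule fixed blind to outcomes, it is 5%. The inflation is therefore conditional; the missing rule is not. It should be corrected before unblinding, because wording added afterwards cannot show that the choice was made without knowledge of the results.

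**What to change.** Before unblinding, replace the endpoint definition with wording such as:

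> The Aim I primary endpoint is change in CFR by PET from month 0 to month 12. Change in sMBF by MRI is the first secondary endpoint, tested at two-sided 0.05 only if CFR is significant at two-sided 0.05 in the designated primary analysis. A PET result missing for any reason, including a scan omitted under the COVID-19 plan, is handled by the missing-data method and is not replaced by sMBF.

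Name that one primary analysis, since the text offers both a t-test or Wilcoxon test and a mixed model with multiple imputation. Reword hypothesis a of Specific Aim I to match.

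If another meaning was intended, write it down instead:

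- **Substitution:** a switch for the whole trial, triggered only by a blinded count of paired PET scans.
- **Two alternative primaries:** Hochberg, or 0.025 each with the detectable differences restated. At 0.025 each with 34 per arm these are 0.81 SD, or 0.75 for CFR, and CFR power at 0.69 falls to about 78%.

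**Cost.** Wording only, with no new data. CFR keeps 85% power at 0.69 if 68 subjects have evaluable PET. With assumed counts of 30 or 26 per arm, power is about 81% or 75%, and the detectable difference is 0.73 or 0.79. sMBF loses stand-alone primary status. Its power to be confirmed in sequence, if both effects are as planned, is:

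| Per arm | ρ = 0.5 | ρ = 0.9 |
|---|---|---|
| 34 | 76% | 81% |
| 30 | 69% | 76% |
| 26 | 61% | 69% |

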
Aim II: For this aim, the endpoint is change in myocardial ECV assessed by myocardial T1 mapping on cardiac MRI. Secondary endpoints will include the following: change in plasma IL-6, MCP-1, sCD163, sCD14 and serum hsCRP, galectin-3, cardiotrophin 1, lipocalin, PINP, PIIINP, BNP. Statistical algorithms as detailed in Aim I will be applied to

Mineralocorticoid Receptor Antagonism for Cardiovascular Health in HIV The MIRACLE HIV Study

these specific endpoints. Similar to Aim I, changes in ECV and inflammatory/fibrosis biomarkers over 12 mos comparing eplerenone vs. placebo will be assessed using ITT and longitudinal linear effects modeling with imputation and sensitivity analyses. By regression techniques and covariate analyses, we will also assess whether improvements in ECV from MR blockade will relate to improvements in diastolic strain.

Sample Size Determination: Thiara et al. show mean \pm SD ECV 0.28 ± 0.04 vs. 0.26 ± 0.03 in HIV vs. non-HIV using cardiac MRI.³⁰ To estimate the SD of change in ECV, we assumed an intrasubject longitudinal correlation over time $r=0.7$ among the HIV group, which results in a conservative SD estimate of 0.03. Based on this SD, the proposed study, with a revised sample size of 80 subjects and therefore 68 evaluable subjects considering a 15% attrition rate, will attain 85% power at a two sided α of 0.05 to detect a difference of at least 0.02 in longitudinal means of ECV. Thus our study is well powered to find a significant difference between arms that is clinically relevant, as each 0.03 increase in ECV raises the risk for mortality or CV morbidity by 50%.²³ For biomarkers, we have 85% power at a two-sided 0.05 α level to show a change of at least 0.74 SD comparing eplerenone vs. placebo.

Aim III: For this aim, the endpoint is change in noncalcified plaque volume assessed by coronary CTA. Secondary endpoints will include: change in high risk plaque morphology (numbers of low attenuation and positively remodeled plaque) by coronary CTA.

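### Imaging endpoints are compared as unadjusted change scores and the covariates are left to baseline tests; fixing a baseline- and strata-adjusted model in advance is a cheap gain in precision and prespecification

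*Combined protocol and SAP*

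**What the plan says.** All references are to Section VI, Biostatistical Analysis, unless stated otherwise.

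- **Main comparison (Aim I).** "We will compare the change in CFR from months 0 to 12 between treatment groups (eplerenone vs. placebo) using student's t-test", or a Wilcoxon rank sum test if the variable is not normal. No covariates enter. Aims II, III and V apply the same algorithms to ECV, noncalcified plaque volume and TBR.
- **ITT and missing data (Aim I).** A "longitudinal linear mixed effects model analysis with random subject level intercepts and time slopes", testing time x treatment on multiply imputed data. The text does not say whether the two arms share a common baseline mean.
- **Covariates (Aim I).** Baseline variables are compared between arms, and "any variable that is statistically different between groups will be controlled for using multivariable modeling". Then: "Covariates that will be considered for inclusion in modeling, include variables that differ at baseline", followed by demographic, cardiovascular, metabolic and HIV variables and compliance. The stated purpose is explanatory: "This will permit us to assess relevant factors that may mediate the effect of eplerenone on CFR in HIV". The plan does not say that this list stays out of the efficacy estimate.
- **Randomisation (Biostatistician Role, and Section IV).** Allocation is 1:1 "using a permuted block algorithm, stratified for gender, statin use, and presence of plaque". Of these three factors only gender is on the candidate list, and no analysis commits to any of them.
- **Sample size (Aims II and V).** For ECV, "we assumed an intrasubject longitudinal correlation over time" of 0.7. For TBR the assumed correlation is 0.75.

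**The concern.** There are two separate matters.

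**Precision.** With 68 evaluable subjects (36 for TBR), a change score fixes the weight on the baseline value at one. ANCOVA estimates that weight, so when the baseline-to-12-month correlation is below one and the SDs are equal, its variance is smaller. The data needed are already collected.

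**Prespecification.** The only firm covariate rule depends on which baseline tests happen to reach significance, and the remaining covariates are optional. One of them, compliance, is measured after randomisation. The adjusted estimate is therefore not fixed in advance, while factors that are fixed in advance (the outcome's baseline value and the strata) are not guaranteed a place in the model.

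**Working it through.** **1. The plan's own figures under the planned t-test** (noncentral t, two-sided 0.05, 34 per arm, or 18 per arm for TBR)

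- CFR, difference 0.69, SD 0.93: 85.4% power. The stated 85% reproduces.
- Plaque, 13.3 mm³, SD 18: 85.1%. Reproduces.
- ECV, 0.02, SD 0.03: 77.3%. The difference giving 85% power is 0.0221.
- TBR, 0.32, SD 0.34: 78.3%.

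The ECV and TBR gaps from 85% are sample-size matters, separate from this point. They serve here only as starting values.

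**2. Large-sample variance ratio, ANCOVA to change score**

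With visit SD s equal at both times, the change score has variance 2(1-r)s² and the ANCOVA residual is (1-r²)s². The ratio is (1+r)/2.

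- ECV, r = 0.70: 0.85.
- TBR, r = 0.75: 0.875. The stated change SD of 0.34 does not match this r, since 0.45 x √(2 x 0.25) = 0.318. It implies r = 1 - 0.34²/(2 x 0.45²) = 0.71, with ratio 0.857. Both values are carried forward.

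**3. Cost of estimating k covariates**

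Multiply by 1 + k/(n-3-k). Here k = 1 is baseline alone, and k = 4 is baseline plus three strata with no prognostic value and no forced balance.

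| Endpoint | k = 1 | k = 4 |
|---|---|---|
| ECV, n = 68, r = 0.70 | 0.85 x (1 + 1/64) = 0.863 | 0.85 x (1 + 4/61) = 0.906 |
| TBR, n = 36, r = 0.75 | 0.875 x (1 + 1/32) = 0.902 | 0.875 x (1 + 4/29) = 0.996 |
| TBR, n = 36, r = 0.71 | 0.857 x (1 + 1/32) = 0.884 | 0.857 x (1 + 4/29) = 0.976 |

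A simulation with 40,000 trials per setting gave ECV reductions of 14.1% and 9.1%, and TBR reductions (r = 0.75) of 9.6% and 0.1%. Strata balanced by the blocked randomisation cost less: a second simulation, with assumed stratum prevalences, gave a ratio of 0.868 for ECV with baseline plus strata.

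**4. ECV in power terms** (change SD 0.03, difference 0.02)

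Power goes from 77.3% to 83.0% (k = 1) or 81.1% (k = 4). The difference detectable with 85% power falls from 0.0221 to 0.0206 or 0.0211. Equivalent sample sizes are 68/0.863 = 79 and 68/0.906 = 75. With the unrounded change SD, 0.04 x √0.6 = 0.031, power goes from 74.6% to 80.6% or 78.6%.

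**5. Sensitivity to unequal SDs**

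Let q be the 12-month SD divided by the baseline SD. The large-sample ratio is q²(1-r²)/(1+q²-2rq). For ECV:

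- q = 0.8: 0.3264/0.52 = 0.628, a gain of 37%.
- q = 1.25: 0.797/0.8125 = 0.981, a gain of 2%.

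**6. The mixed model**

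With two complete imaging times and a free treatment main effect, the time x treatment term is the difference in mean change, which is the change-score contrast. Simulated ECV trials with unstructured covariance confirmed this to rounding error. Constraining the baseline means to be equal gave a variance ratio of 0.862. With 12 of 80 subjects missing at 12 months, the ratios were 0.980 (free) and 0.861 (common mean). An unstated modelling choice therefore decides whether the precision is gained.

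**7. The baseline-test rule**

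ECV was simulated with 12 independent candidates explaining 0 to 50% of the change variance. Power was 75-77% under the rule, 76-77% for the t-test and 82-83% for ANCOVA on baseline. Null rejection was 3.7-4.7%.

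**The case against.** The planned test is valid, matches the change endpoints and the sample-size basis, and is itself fixed: the covariate rule governs the multivariable models, not the t-test. The longitudinal model could already be as precise as ANCOVA. The gains are modest, and for TBR the strata can use them up. For plaque volume, baseline volume and plaque presence overlap heavily. All of this stands. It sets the weight of the point but does not remove it, because neither the baseline-mean constraint nor the adjusted model is written down.

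A reader might infer more than the documents support:

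- **That the plan wastes the correlation.** It does not. Relative to comparing 12-month values alone (variance 1), the ECV change score has 2(1-0.70) = 0.60 and ANCOVA has 1-0.49 = 0.51. The planned test already takes 0.40/0.49 = 82% of the available large-sample gain. For TBR at r = 0.75 it takes 0.50/0.5625 = 89%.
- **That the gain for CFR is large.** Aim I says "we considered the range 0.73 - 0.93 SD to accurately reflect the potential variability of change in CFR". Taking 0.73 as the SD at each visit gives r = 0.50 for a change SD of 0.73 and r = 0.19 for 0.93, hence apparent gains of 24-40%. But 0.73 is a cross-sectional SD reused as a change SD, which forces r = 0.50 by algebra. The 0.93 comes from a 6-month study in diabetics. Neither tells us the 12-month correlation of CFR in this population.
- **That chance imbalance will trigger adjustment at a known rate.** Twelve independent candidates would give 1 - 0.95^12 = 46%, but the rule covers baseline variables generally, gender is balanced by design, and lipids, glucose and BP are not plausibly independent.
- **That the rule biases the trial or inflates type I error.** The simulation shows no inflation.

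**Conclusion.** The point holds as a free or cheap improvement; the plan contains no error here. The change-score comparison is valid and unbiased but somewhat less precise than a baseline-adjusted one, and the adjusted model is not fixed in advance. The prespecification argument is the firmer of the two, because it does not depend on any assumed correlation.

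The ECV gain (about 14%, or at least about 9% with non-prognostic strata) and the TBR gain (about 10-12%, or 0-2%) rest on equal SDs at both visits and on the plan's own correlations. Prognostic strata would raise the lower figures. A 12-month SD larger than baseline would shrink all of them, to about 2% in large samples for ECV at a ratio of 1.25. The documents give no within-subject correlation for CFR or plaque, so no gain is claimed there.

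**What to change.** In Section VI:

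- Prespecify, as the primary analysis of each imaging endpoint, an ANCOVA of the 12-month value on treatment, baseline value, gender, statin use and plaque presence, with the planned multiple imputation. Alternatively, keep the planned longitudinal model, state that baseline means are constrained equal, and add the strata.
- For TBR, adjust at least for baseline and leave the strata optional.
- For skewed plaque volume, use the transformation that Aim I already allows, or a rank-based ANCOVA.
- Delete the baseline-significance rule. Restrict the candidate list, including compliance, to explanatory analyses. Keep the t-test and Wilcoxon as supportive.

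The cost is SAP wording and up to four degrees of freedom (68 - 6 = 62 residual for ECV), with no new data. If the strata are not prognostic they give back part of the gain, and in the TBR substudy possibly nearly all of it.
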